# 9.5 IRB/IEC Notification of Serious Adverse Events and Other Unanticipated Problems

The investigator will promptly notify the IRB of all on-site unanticipated, SAE's that are related to the research activity. Other unanticipated problems related to the research involving risk to subjects or others will also be reported promptly to the IRB. Written reports will be filed using the eIRB system and in accordance with the timeline below. External SAE's that are both unexpected and related to the study intervention will be reported promptly after the investigator receives the report.

Type of Unanticipated Problem	Initial Notification (Phone, Email, Fax)	Written Report
Internal (on-site) SAEs Death or Life Threatening	24 hours	Within 2 calendar days
Internal (on-site) SAEs All other SAEs	7 days	Within 7 business days
Unanticipated Problems Related to Research	7 days	Within 7 business days
All other AEs	N/A	Brief Summary of important AEs may be reported at time of continuing review

## 9.5.1 Follow-up report

If an SAE has not resolved at the time of the initial report and new information arises that changes the investigator's assessment of the event, a follow-up report including all relevant new or reassessed information (e.g., concomitant medication, medical history) should be submitted to the IRB. The investigator is responsible for ensuring that all SAE's are followed until either resolved or stable.

## 9.6 Investigator Reporting of a Serious Adverse Event to Sponsor

Reporting will be consistent with regulatory and sponsor requirements.

## 9.7 Medical Emergencies

If a medical emergency occurs during the screening process, the subject will immediately be referred to the CHOP or HUP emergency department. If the study coordinator or investigators learns of a medical emergency while communicating with a subject who is not on-site, the subject will immediately be referred to a local hospital emergency department.

## **10 STUDY ADMINISTRATION**

## **10.1 Treatment Assignment Methods**

#### **10.1.1 Randomization**

The study biostatistician, [name], will generate a randomization schedule that will be implemented in the randomization module of the study database system. The randomization scheme will be based on equal allocation of BCAA's to placebo and stratified based on sex. Upon confirmation of eligibility in the DMS, the randomization module will be programmed to generate a randomization number that corresponds to a unique kit number of BCAA or placebo treatment. This kit number will be used to distribute treatment.

## 10.1.2 Blinding

All primary study team members will be blinded to treatment arm. The Database Administrator will have access to the information that links the kit number to the treatment arm. He/she will provide this information to the Investigational Drug Service (IDS) so that kits are prepared according to this scheme. BCAA and placebo treatment kits will appear identical. They will be labeled with the following information:

- 1. Kit number
- 2. Study name and number
- 3. Bottle # X of 42.
- 4. Subject ID # [blank line to record this number]

## 10.1.3 Unblinding

Unblinding can occur if the PI instructs the IDS to reveal this information. A direct request from the PI to IDS must be documented.

#### **10.2 Data Collection and Management**

Procedures to assure confidentiality will be strictly observed. All identifiable personal health information (PHI) data will be 1) kept in confidential locked files; 2) identified by subject number only; and 3) kept separately from identifying information used for subject tracking and follow-up contact. Identifying information will be kept in separate locked files. No identifying information will be disclosed in reports, publications, or presentations.

Protection of subjects depends on the joint activities of all clinical staff as well as the database administrative team. Extensive efforts will be made to ensure that subjects' confidentiality is maintained. Each subject will be assigned a unique study identification number and is never tracked through the study by name, medical record number, or any other personal identifier. A log of the subject names, ID numbers, and pertinent registration information (e.g., home address, telephone number, and emergency contact information) is maintained in a separate, locked area at the clinical site. The database administrative staff will not have access to this information. Only the subject ID number and date of birth are given to the database administrative staff and registered in the study database. Any communication between the database administrative staff and investigators regarding subject

04/06/2018 V 0.16

data will occur via the subject ID number. Any forms or documents sent to the IRB or other regulatory authorities will have all personal information removed.

Study data will be entered into a web based data management system (DMS). This DMS uses a secure connection between the client browser at the clinical site and the web server at the Penn Clinical Research Computing Unit (CRCU). Data transmitted over this connection is authenticated by the use of digital certificates and is encrypted as it travels the internet to the CRCU. Data is being gathered and stored through the CRCU because the expertise of the CRCU staff was required to construct the secure website subjects will access to complete daily assessments and to build the DMS on an Oracle platform so it can communicate in a subject-specific manner directly and securely with the Axon Sports system. The Oracle development tools integrate seamlessly with the DMS to allow a full range of programming functionality which allow us to: 1) capture data from remote locations over the internet using secure connections, 2) incorporate data quality checks at entry and after entry using simple or complex rule sets as needed, 3) assign specific privileges for users to reflect their role and needs on the project, to provide an electronic audit trail of all data changes, 4) incorporate and enforce workflow logic where appropriate, 5) integrate with external data and software systems, and 6) provide secure and convenient access to data for authorized study personnel. Using this platform, the DMS automatically transmits a subject's ID number and date of birth to the Axon Sports system. The Axon Sports system then securely sends coded data to the DMS where it is stored. At no point is PHI except date of birth (for the purposes of computing a participant's age) collected by the Axon Sports system or stored in the DMS. The Axon Sports system does not have direct access to the DMS. All information transmitted between the Axon Sports system and the DMS is coded solely by subject ID number.

The DMS will be designed to prevent unauthorized access to trial data and to prevent data loss due to equipment failure or catastrophic events. The procedures to do so encompass user account management, user privilege assignment, data loss prevention (database backup), computer systems validation, performance monitoring, and the DMS change management. User access will be controlled by assignment of confidential usernames, passwords, and role assignment. The system will meet the applicable Federal regulatory requirements and those described in the E6 Good Clinical Practice Guidelines to ensure the confidentiality of trial subjects.

CRCU data networks comprise a set of physical data networks all linked in a point-to-point configuration to form a single logical data network. The network is protected through the use of several Juniper® firewall devices. These devices perform as firewalls and logging devices for data network traffic, as Intrusion Detection to alarm information technology personnel to possible network attack scenarios, and as an email spam filter and eliminator.

Security requirements at the computer systems' level start with separation of duties with the system administrators. Administrators each are assigned specific accounts that dictate what services they have access to. All accounts are individually assigned and logged, regardless of access level. The systems are configured to vendor specification with the published operating system releases and published patches, before connected to any data network. Once configured, the systems operating system is imaged and TripWire® software is loaded  $04/06/2018 \vee 0.16$ 

to ensure all system and operating files maintain their current configurations. Any changes to the recorded and monitored files results in an alert being sent to the responsible administrator.

All users of the database applications have unique and permanent user identifications assigned to them for use to gain access to the systems and to the appropriate databases. Passwords are aged and also restricted so good password creation and usage are enforced. Users are trained on log-in procedures and also application usage. A support helpdesk is maintained during normal business hours to ensure problems are quickly discovered and resolved for the users.

The data is stored in several disk storage subsystems that are backed up and stored off site, depending on the critical nature of the data. Standard operating procedures are in place to provide business continuity, disaster recovery, and file restoration. All hardware/system software components are covered by vendor supported maintenance contracts with a 4-hour or less turn-around on parts and assistance.

Computer system security will be enhanced for the applications through the use of the Oracle database repositories. Users of the applications will not be allowed to log into any of the project servers directly. All users of the project will only log into specific applications where access is controlled and limited.

#### 10.3 Confidentiality

Patient confidentiality will be maintained at all times and study information will be protected against release to unauthorized people. All data and records generated during this study will be kept confidential in accordance with institutional policies and the Health Insurance Portability and Accountability Act (HIPAA) on subject privacy. The investigator and all other personnel will not use such data and records for any purpose other than conducting the study. Subjects will be assigned study numbers for entry into the protocol; this number alone will identify them. Subjects are free to refuse participation in the study and can withdraw at any time without compromising clinical care. The investigator will obtain a data use agreement between the provider (the PI) of the data and any recipient researchers (including others at CHOP) before sharing a limited dataset (PHI limited to dates and zip codes).

#### **10.4 Regulatory and Ethical Considerations**

#### 10.4.1 Data and Safety Monitoring Plan

[name], an experienced neurologist, will act as the independent Medical Monitor for adverse events during this study. [name] has served in prior and ongoing clinical trials as endpoint adjudicator and was on the Clinical Event Committee for the pediatric EXCOR Berlin heart trial. She is presently a member of the endpoint adjudication committee for the Thrombolysis in Pediatric Stroke trial. The Medical Monitor will review all acute AE's regardless of how the investigator reports the relationship between the event and the study intervention. All patient deaths will be similarly reviewed. The study will also undergo monitoring by the CHOP Office of Research Compliance and Regulatory Affairs after each subject for the next six subjects enrolled and then at least annually throughout the duration of the study.

#### 10.4.2 Risk Assessment

Risks for this study are a minor increase above minimal. Subject safety will be monitored by AE's on a weekly basis. Expected adverse experiences during this study may include gastrointestinal symptoms such as dyspepsia either from the BCAA's themselves or the 20 ounces of fluid consumed. Prior studies have shown that these symptoms when related to BCAA's are mild and transient. An informal inquiry of athletes (both male and female) from many sports indicated that drinking 20 ounces of fluid twice daily is not burdensome and within the volume typically consumed while training or competing. Should a subject report new onset gastrointestinal symptoms while on therapy, the subject will be monitored to see if these symptoms either have an alternative explanation (e.g. development of acute gastroenteritis from an identifiable source) or spontaneously resolve in less than 24 hours. The study therapy will not be held unless these symptoms persist for more than 24 hours or are severe enough to require medical attention. In this case the subject will be removed from the study and the therapy not restarted. Taking the CCAT or CDP may temporarily exacerbate concussion symptoms, which typically resolve after a short period of rest. Neurological and psychiatric symptoms induced by changes in neurotransmitters like serotonin, dopamine, norepinephrine are theoretically possible with BCAA therapy but have never been observed clinically. Emergence of any of these symptoms will result in discontinuation of the subject's participation in the study. BCAA therapy will be discontinued for any SAE related to its use.

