# 4.3.2 Total Number of Study Sites/Total Number of Subjects Projected

The study will be conducted through the Children's Hospital of Philadelphia and the Hospital of the University of Pennsylvania. Recruitment will stop when 50 subjects who are evaluable for efficacy are enrolled. A subject who is evaluable for efficacy is one who completes the study up until at least day 10 of the study. It is expected that approximately 72 subjects will be enrolled to produce 50 such subjects. All subjects who enroll and receive study medication will be evaluable for safety.

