#### 5.5 Rescue Medication Administration

Subjects who experience side effects from the study medication, to a level that the subject requests medication to manage these symptoms, will be discontinued from the study.

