#### 5.6 Subject Completion/Withdrawal

Subjects may withdraw from the study at any time without prejudice to their care. They may be discontinued from the study at the discretion of the investigators for safety concerns related to any adverse event. Any subject who sustains a second concussion during the study period will be withdrawn. Additionally, any female subject who becomes pregnant while enrolled in the study will be withdrawn. Date of termination will be documented for each subject.

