# 5.7 Early Termination Study Visit

The study coordinator will contact subjects who terminate early and request that they return all of the study drug bottles (used and unused).

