## 7.3.2 Primary Efficacy Analysis

The primary intent to treat analysis will include all subjects who enroll and contribute at least 10 days of data to the study. The mean trajectory in decline and recovery in processing speed is unknown. Thus the primary analysis will aim to determine whether there are differences in processing speed between the BCAA dose groups and placebo, and if so, at what time periods the differences are most pronounced. The primary analysis will focus on results for the first 10 days of the study when we anticipate that the majority of subjects will be highly compliant. We will model processing speed as a function of dose and day of study and will allow differences between dose groups to vary as a function of time through a series of interaction terms. To ensure that the number of interaction terms does not become too large, we will consider groups of two to four time points, looking specifically at whether

04/06/2018 V 0.16

there are differences between any of the dose groups and placebo at Days 1-2, 3-6, 7-10, 11-14, 15-18, 19-21. The primary analysis will consider three key time periods, Days 3-6, 7-10 and 11-14 when we expect differences in processing speed between the BCAA-treated groups and placebo to be largest. Since processing speed differs with age, the model will be adjusted for age to account for any imbalances in age between dose groups. A mixed effects model will be used to account for correlations between repeated measurements on individual subjects. Likelihood ratio tests will be employed to specifically test whether there are differences in mean processing speed between placebo and any of the BCAA doses at the three key time periods. These three global tests will be conducted at a family-wise error rate of 0.05, using a Bonferroni correction to account for the three individual global tests. If statistical significance is achieved for the global test, we will then compare individual dose levels to placebo within time periods, again using a correction for four multiple tests per key time period.

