We note that with five treatment groups and 21 time points, there are a very large number of possible hypothesis tests that can be carried out with these data. If all of these tests were carried out without adjusting for multiple comparisons, we would undoubtedly find spurious associations. On the other hand, adjusting for large numbers of multiple comparisons substantially reduces the statistical power of a study. By focusing our testing for the primary efficacy analysis on three key periods where we adjust for a limited number of tests, we balance the need for a rigorous statistical testing procedure with a need to maintain statistical power.

An analysis of the Day 1-2, 15-18 and 19-21 data will follow the same format, but will be considered secondary and will not be formally corrected for multiple testing. In addition to hypothesis testing, we will estimate and plot means and confidence intervals for each group at each time point. This analysis will guide the recommendation for dose levels and evaluation times for the primary analysis in future efficacy studies.

With concerted efforts from our study coordinators and study staff we are hopeful that we can maintain excellent compliance throughout the study. In particular we expect good compliance early in the study when patients are highly motivated to feel better and return to school, work and play. However, we allow that some patients may have difficulty with compliance due to their injury, or become non-compliant once their symptoms improve. As part of this feasibility study, we will explore patterns of missing data, in particular how they may relate to the observed response (e.g. more missing data in those subjects who show better or worse processing speed) to compliance (e.g. more missing data in subjects who regularly fail to consume their supplements) and to demographics e.g. gender, age. This information will be valuable in planning future efficacy trials, and will guide our efforts to adjust for missing data. For example if the probability of missing data is associated with outcome, then non-ignorable missing data methods will be needed, whereas missing at random assumptions will be valid if the missing data can be explained by covariate information.

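### The primary analysis called intent to treat drops every randomized subject with fewer than 10 days of data, and some of those losses may be caused by the treatment

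*Combined protocol and SAP*

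**What the plan says.** **Analysis set.** Section 7.3.2: "The primary intent to treat analysis will include all subjects who enroll and contribute at least 10 days of data to the study". Sections 4.3.2 and 7.4 use a similar threshold for being evaluable for efficacy, namely staying in the study to at least Day 10. Section 4.3.2 adds "Recruitment will stop when 50 subjects who are evaluable for efficacy are enrolled", with about 72 enrolments expected to reach that number.

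**Rules that end study participation.**
- Section 10.4.2, gastrointestinal symptoms lasting more than 24 hours or needing medical attention: "In this case the subject will be removed from the study and the therapy not restarted".
- Section 10.4.2, neurological or psychiatric symptoms thought to arise from neurotransmitter changes under BCAA: "Emergence of any of these symptoms will result in discontinuation" of participation.
- Section 5.5, subjects with side effects "to a level that the subject requests medication to manage these symptoms, will be discontinued from the study".
- Section 5.6, at discretion only: "They may be discontinued from the study at the discretion of the investigators for safety concerns related to any adverse event".

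One rule is different. The last sentence of 10.4.2 says that a related serious adverse event stops BCAA therapy, and it does not mention removal from the study.

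**After early termination.** Section 5.7 has the coordinator ask for used and unused bottles. It describes no further outcome collection.

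**Missing data.** Section 7.3.2 says "we will explore patterns of missing data", relates them to response, compliance and demographics, and foresees non-ignorable methods if missingness depends on outcome. It specifies no analysis that restores the excluded subjects.

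**The concern.** An intent-to-treat comparison is protected by randomization because membership is settled before treatment can act. Here membership depends on what happens afterwards, so the groups compared are those who stayed and supplied enough data. If staying depends on both dose and recovery, the dose-placebo contrasts are no longer purely randomized comparisons.

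The filter applies to every early loss, whether from poor compliance, recovery, loss of interest or side effects. Side effects deserve separate mention because they are the one cause that the protocol itself ties to treatment, and they can differ by dose. Nausea is also both a gastrointestinal symptom and an item on the concussion checklist (section 6.2.2, Appendix 1), so removal could also track recovery.

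What is at stake is the trial's stated purpose of finding which dose looks most promising (section 3) and guiding dose levels and evaluation times for later efficacy trials (7.3.2). With about 10 evaluable subjects per arm, a few selective losses in one arm could affect that choice.

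**Working it through.** **1. What the filter discards.** The primary windows are Days 3-6, 7-10 and 11-14 (7.3.2). A subject leaving on Day 8 can have complete data for the first window and part of the second. None of it enters the primary analysis, although a mixed model accepts incomplete series.

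**2. Expected losses.** From 4.3.2: 72 - 50 = 22 non-evaluable, and 22/72 = 30.6%. Per arm, 72/5 = 14.4 enrolled and 22/5 = 4.4 lost, if losses are equal. This covers all causes; the documents give no split by cause or arm.

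**3. The plan's own figure.** Inputs from 7.4: SD 0.10, intra-class correlation 0.5, three measurements, 10 per arm, 80% power, two-sided 0.05/4 = 0.0125.
- SD of a subject's window mean: 0.10 × sqrt((1 + 2 × 0.5)/3) = 0.0816 s.
- Standard error of one dose-placebo contrast: 0.0816 × sqrt(2/10) = 0.0365 s.
- Detectable difference: (2.498 + 0.842) × 0.0365 = 0.122 s.

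This reproduces 7.4. The power figure is not in dispute.

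**4. Illustrative shift from adverse-event removals.** The documents give no removal rate, so these are assumptions: a fraction p of BCAA subjects is removed before contributing 10 days of data, none on placebo, and removal has correlation r with slower response. The only rate in the documents is 12% gastrointestinal symptoms in one cirrhosis study, a population that section 2.4 itself calls different. Of 72 × 4/5 = 57.6 BCAA subjects, 6% is 3.5 and 12% is 6.9.

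Shift in the retained BCAA mean = r × 0.0816 × φ(z)/(1 - p), where z is the upper-p normal quantile.

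| p | z | φ(z)/(1 - p) | r = 0 | r = 0.3 | r = 0.5 |
|---|---|---|---|---|---|
| 0 | – | 0 | 0 | 0 | 0 |
| 6% | 1.555 | 0.127 | 0 | 0.0031 s (2.5% of 0.122) | 0.0052 s (4.2%) |
| 12% | 1.175 | 0.227 | 0 | 0.0056 s (4.6%) | 0.0093 s (7.6%) |

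The largest entry is 0.0093/0.0365 = 0.25 standard errors. It would raise the false-positive rate of one contrast from 1.25% to about 1.5%.

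**5. Sensitivity to placebo removals.** With 6% removed on placebo as well, the 12%, r = 0.5 shift becomes 0.0093 - 0.0052 = 0.0041 s.

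**6. All-cause boundary case.** If the whole 30.6% loss were selective in one BCAA arm and absent on placebo, the same formula gives 0.012 s at r = 0.3, 0.021 s at r = 0.5 and 0.029 s at r = 0.7, or about 10% to 24% of 0.122 s. With equal rates and equal correlations in both arms the contrast shifts by zero. The documents do not say where between these cases the trial would fall.

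**7. Precision.** If all 72 gave complete data, the detectable difference would be 0.122 × sqrt(10/14.4) = 0.102 s. That is an upper bound on the gain. Early leavers supply partial series, so the real gain is smaller.

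**The case against.** The study calls itself exploratory and a feasibility study. All treated subjects stay in the safety analysis (4.3.2, 7.3.4), and outcome-related missingness is to be examined and used to guide adjustment. Section 10.4.2 warns that the cognitive test may temporarily worsen symptoms, so sparing unwell subjects, some of them minors, is a defensible protective choice. These points stand. They weigh on the adverse-event rules more than on the filter, because using data already collected burdens nobody.

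The upper end of the adverse-event illustration also stacks assumptions. The 12% is a rate of any such symptoms, whereas removal requires persistence or medical attention, and 10.4.2 calls BCAA-related symptoms mild and transient. The same section says that the neurological and psychiatric symptoms have never been seen clinically. Zero removals on placebo is generous: 10.4.2 also blames the fluid volume, which every arm drinks, and the placebo contains 30 g of microcrystalline cellulose (8.1.3). A subject removed after contributing 10 days of data stays in the analysis. The calculation uses one pooled BCAA rate and does not model a dose gradient. All of this stands, and it is why the adverse-event part is judged small.

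A reader might infer that every adverse event ends participation. The documents do not say so: section 5.6 is discretionary, and the related serious-event rule stops only therapy. A reader might also infer that side effects are the main source of exclusion, or that dose-related bias is established. The documents give no removal rate by arm, and the difficulty they do describe is compliance (5.2, 7.3.2).

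**Conclusion.** The concern holds for the analysis set. The primary analysis is not intent to treat: it conditions on a post-randomization event, discards usable data, and is expected to exclude about 22 of 72 subjects. Exploring missing-data patterns does not by itself put back the data that the filter removes, and no method recovers outcomes that were never collected.

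The size and direction of any bias are unknown. The adverse-event part is probably small and possibly zero: 0 to 0.009 s under the stated assumptions, at most about 8% of the detectable difference and a quarter of a standard error. The all-cause range of 0.012 to 0.029 s is a boundary case that requires one-sided selective loss, and it should not be read as an estimate.

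A material dose-related bias, or a sample-size error, might be inferred; neither is supported. The 0.122 s stands as the figure for 10 evaluable subjects per arm. The change is still worth making because its main part costs almost nothing and removes an avoidable selection step.

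**What to change.** **Main change, section 7.3.2.** Fit the primary mixed model to all available post-randomization data from all randomized subjects, in their randomized arm, without the 10-day requirement. Keep the at-least-10-days set as a sensitivity analysis. This needs only a change to the analysis text and no new data.

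**Secondary change, sections 10.4.2, 5.5, 5.6 and 5.7.** State that these adverse events stop the drink, and that subjects who agree and who tolerate testing may continue the existing web assessments to Day 21. Withdrawal of consent ends collection. Add a sensitivity analysis that excludes off-drink days. The psychoactive-medication rule (5.4) and the second-concussion and pregnancy withdrawals (5.6) can stay as they are.

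**Clarification, section 4.3.2.** State whether off-drink subjects who reach Day 10 count toward the 50 evaluable.

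**Costs.** The secondary change needs a protocol amendment but no added visits. It adds a modest testing burden in a study that already calls its data collection onerous (5.2). Off-drink days may dilute a true effect, which the sensitivity analysis would help to show. The tolerability condition leaves some missingness related to how unwell a subject is, so the selection is reduced and not removed. Subjects already enrolled were followed under the existing rules, and the report should say so.
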